9 LIST OF TABLES AND TABLE SHELLS

If not otherwise specified, tables will be repeated for each combination of treatment and indication.

Table No.	Title	Treatment/ Indication	Analysis set	Description
1	Demography and Baseline Characteristics			
1.1	Disposition of patients			
1.1-1.1	Number of patients screened and reason for Non-inclusion	All	All patients	Counts over all treatments and indications (total number of patients in Star-Tor, total number of patients by indication, total number of patients by indication and treatment, total number of patients by indication and treatment sequence.
1.1-1.2	Treatment sequences	mRCC	All patients	Frequency table for sequences
1.1-1.3	Age of patients screened	All	Safety	Sample statistics for patients included and patients not included
1.1-2	Number of centers and patients planned and realized	All	Safety	number centers planned:200; number patients planned: 100
1.1-3	Number of patients per center	All	Safety	include number of active centers (e.g. at least 1 subject included)
1.1-4	Reason for premature discontinuation	All	Safety	Frequency tables for major reasons and specifications
1.1-5.1	Study duration	All	Safety	First patient in / Last patient out
1.1-5.2	Study periods	All	Safety Sequence analysis	Duration of study periods (Treatment phase, survival follow-up, sequence 1, sequence 2)
1.1-6.1	Summary of patient disposition	All	Safety	Patients who - were included into the study - were included into the Safety set - were included into the Safety set documented under prior versions of protocol - were included into the EAS - were included into the EAS documented under prior versions of protocol - Reason for exclusion from analysis set (refers to most comprehensive analysis set)

Table No.	Title	Treatment/ Indication	Analysis set	Description
1.1-6.2	Number of patients by time window	All	Safety, EAS	.1 Number of patients by visit .2 Number of visits by time window (table may be omitted, if only very few documented visits were condensed into one time window)
1.2	Demography			
1.2-1	Demographic variables	All	Safety, EAS Sequence analysis	age, sex, body height
1.2-2	Time-varying demographic variables	All	Safety, EAS Sequence analysis	Weight, BMI by time window
1.3	Medical and oncological history			
CCI				
CCI				
1.3-1.3	Current manifestations	MCL	SAFETY, EAS	Frequency tables for locations of manifestations
1.3-1.4	Tumor anamnesis - other information	GIST	SAFETY, EAS	.1 Frequency table for size of primary tumor, sample statistics for number of mitoses, frequency table for primary mutation analysis performed?, frequency table for type of KIT-mutation .2 Frequency table for mutation analysis performed in recidive?, frequency table for type of mutation
CCI				
1.3-3	ECG	mRCC, GIST	SAFETY, EAS	Frequency tables for normal/abnormal ECG by time window

Table No.	Title	Treatment/ Indication	Analysis set	Description
CCI				

Table No.	Title	Treatment/ Indication	Analysis set	Description
CCI				
				, number of transplantations, R0 resection reached

Table No.	Title	Treatment/ Indication	Analysis set	Description
CCI				

Table No.	Title	Treatment/ Indication	Analysis set	Description
CCI				
2	Effectiveness			
2.1	Response to therapy			
2.1-1	Course of response to therapy	All	EAS	Frequency table by time window (in total and by patient risk groups)

Table No.	Title	Treatment/ Indication	Analysis set	Description
2.1-2	Best response	All	EAS	Frequency table for best response in total and confirmed / not-confirmed (the latter not for Torisel® MCL); Frequency table for best response excluding patients "not assessable" only for MCL Listing of reasons for not assessable best response; Frequency table for best response by patient risk groups
2.1-3	Used diagnosis technique	All	EAS	CT, Thorax X-ray, MRT, Ultrasonic testing, PET, Bone scan, Clinical (by time window and for best response)
2.2	Overall survival			
2.2-1	Kaplan-Meier estimates for Overall survival	All	EAS Sequence analysis	Time to 25%, median and 75% survival with confidence intervals incl Kaplan-Meier curve on all patients
2.2-2	Kaplan-Meier estimates for Overall survival by patient risk groups	mRCC	EAS	 .1 Physicians prognosis of patients risk .2 Risk groups according to Motzer score .3 Risk groups according to modified Motzer score .4 Risk groups according to Motzer score for pretreated patients .5 by treatment sequence .6 by treatment and treatment line. .7 1st line patients by risk (poor vs. non-poor) .8 by LDH ≤ 300 U/l vs > 300 U/l incl. Log-ranktest and Kaplan-Meier curves

Table No.	Title	Treatment/ Indication	Analysis set	Description
2.2-2	Kaplan-Meier estimates for Overall survival by patient risk groups	MCL	EAS	.1 Risk groups according to MIPI score at time of primary diagnosis .2 Risk groups according to current MIPI score .3 2 nd and 3 rd line .4 2 nd to 4 th line .5 4 th line and beyond .6 5 th line and beyond .7 Patients with OR (CR+PR) .8 Patients with (MR + SD) .9 Patients with clinical benefit (CR+PR+MR+SD) .10 Patients ≤ 65 vs. patients > 65 yrs. including Kaplan-Meier curves .1 OS all patients excluding "not assessable" patients .2 OS patients with OR (CR+PR) vs. (MR+SD) vs. PD .3 OS patients with clinical benefit (CR+PR+MR+SD) vs. PD .4 OS Temsirolimus 2 nd to 4 th line (1 − 3 prior therapies) vs. 5 th line and beyond (≥ 4 prior therapies) .5 OS 2 nd to 3 rd line Temsirolimus (1 − 2 prior therapies) vs. 4 th line and beyond (≥ 3 prior therapies)
2.2-2	Kaplan-Meier estimates for Overall survival by patient risk groups	GIST	EAS	.1 Risk groups according to Fletchers risk table .2 Risk groups according to physician's prognosis
2.2-3	Frequency table of patients status by time window (survival phase)	All	EAS	
2.3	Progression free survival			
2.3-1	Kaplan-Meier estimates for Progression free survival	All	EAS Sequence analysis	Time to 25%, median and 75% survival with confidence intervals including Kaplan-Meier curve on all patients

Table No.	Title	Treatment/ Indication	Analysis set	Description
2.3-2	Kaplan-Meier estimates for Progression free survival by patient risk groups	mRCC	EAS	.1 Physicians prognosis of patients risk .2 Risk groups according to Motzer score .3 Risk groups according to modified Motzer score .4 Risk groups according to Motzer score for pretreated patients .5 by treatment sequence .6 1st line patients .7 1st line patients by risk (poor vs. non-poor) .8 2nd line vs. higher lines .9 2nd vs. 3rd line vs. higher lines .10 patients ≤ 65 yrs vs. > 65 yrs .11 by LDH low (≤ 300 U/l) vs high (> 300 U/l) .12 by histology (clear cell vs. other) Kaplan-Meier curves incl Log-Rank-Test .1 PFS 1st line vs. 2nd line and higher .2 PFS 1st line vs. 2nd line vs. 3rd line and higher .3 PFS ≤ 65 yrs vs. > 65 yrs .4 PFS LDH low (≤ 300 U/l) vs high (> 300 U/l) .5 PFS clear cell histology vs. other histology

Description Table No. Title Treatment/ **Analysis set** Indication .1 Risk groups according to MIPI score at time of 2.3-2 Kaplan-Meier estimates for Progression free MCL EAS survival by patient risk groups primary diagnosis .2 Risk groups according to current MIPI score .3 2nd and 3rd line .4 2nd to 4th line .5 4th line and beyond .6 5th line and beyond .7 Patients with OR (CR+PR) .8 Patients with MR + SD .9 Patients with clinical benefit (CR+PR+MR+SD) Kaplan-Meier curves incl. Log-Rank-Test .1 PFS all patients excluding "not assessable" patients .2 PFS patients with OR (CR+PR) vs. (MR+SD) .3 PFS patients with clinical benefit (CR+PR+MR+SD) .4 PFS Temsirolimus 2^{nd} to 4^{th} line (1-3) prior therapies) vs. 5^{th} line and beyond (≥ 4 prior therapies) .5 PFS 2^{nd} to 3^{rd} line Temsirolimus (1 – 2 prior therapies) vs. 4th line and beyond (≥ 3 prior therapies) .1 Risk groups according to Fletchers risk table Kaplan-Meier estimates for Progression free EAS 2.3-2 **GIST** survival by patient risk groups .2 Risk groups according to physician's prognosis Physician's global assessment 2.4 Frequency table by time windows and for the last 2.4 Physician's global assessment of effectiveness mRCC **EAS** documented visit: total and by physician's prognosis of patients risk and by risk groups according to Motzer score, modified Motzer score and Motzer score for pretreated patients. Frequency table by time windows and for the last 2.4 Physician's global assessment of effectiveness MCL EAS documented visit: total and by risk groups according to MIPI score at time of primary diagnosis and

PFIZER CONFIDENTIAL

according to current MIPI score.

Table No.	Title	Treatment/ Indication	Analysis set	Description
2.4	Physician's global assessment of effectiveness	GIST	EAS	Frequency table by time windows and for the last documented visit: total and by physician's prognosis of patients risk and by risk groups according to Fletchers risk table.
2.5	Course of Karnofsky performance status scale			
2.5	Course of Karnofsky performance status scale	mRCC, GIST	EAS Sequence analysis for mRCC	Sample statistics by time windows and for the last documented visit, including absolute and relative differences to baseline (in total and by patient risk groups)
2.5	Course of ECOG performance status and B-symptoms			
2.5-1	Course of ECOG performance status	MCL	EAS	Frequency table by time windows and for the last documented visit, shift table for differences to baseline (in total and by patient risk groups)
2.5-2	Course of B-symptoms	MCL	EAS	Frequency table by time windows and for the last documented visit
2.6	FKSI-15: Course			
2.6-1	Course of FKSI-15 score	mRCC	EAS Sequence analysis	Sample statistics by time windows and for the last documented visit and absolute and relative change to baseline.
2.6-2	Course of FKSI-DRS score	mRCC	EAS Sequence analysis	Sample statistics by time windows and for the last documented visit and absolute and relative change to baseline.
2.6-3	Course of FKSI domains	mRCC	EAS Sequence analysis	Sample statistics by time windows and for the last documented visit and absolute and relative change to baseline.
2.7	EQ-5D: Course			
2.7-1	Course of EQ-5D: domains	mRCC	EAS Sequence analysis	Frequency tables by time window and for the last documented visit and shift tables to baseline
2.7-2	Course of EQ-5D-VAS	mRCC	EAS Sequence analysis	Sample statistics by time windows and for the last documented visit and absolute and relative change to baseline.

Table No.	Title	Treatment/ Indication	Analysis set	Description
2.7-3	Course of EQ-5D: TTO	mRCC	EAS Sequence analysis	Sample statistics by time windows and for the last documented visit and absolute and relative change to baseline.
3	Safety			
3.1	Display of adverse events (AE)			
3.1-1.1	Summary of adverse events	All	Safety	No. / % of patients - at risk - with AE - with drug related AE - with AE related to Pfizer treatment - with AE related to interim treatment - with SAE - with drug related SAE - with SAE related to Pfizer treatment - with SAE related to Pfizer treatment - with SAE related to interim treatment - with AE leading to permanent discontinuation of Torisel®/ Sutent® / Inlyta® - with drug related AE leading to permanent discontinuation of Torisel®/ Sutent® / Inlyta® - with SAE leading to permanent discontinuation of Torisel®/ Sutent® / Inlyta® - with drug related SAE leading to permanent discontinuation of Torisel®/ Sutent® / Inlyta® - with drug related SAE leading to permanent discontinuation of Torisel®/ Sutent® / Inlyta® - Death No. / % of AE - all AE - drug related - related to Pfizer treatment - related to interim treatment - SAE - drug related SAE - SAE related to Pfizer treatment - SAE related to interim treatment

Table No.	Title	Treatment/ Indication	Analysis set	Description
				.1 total .2 by treatment sequence .3 by line
3.1-1.2	Summary of adverse events by concomitant CYP3A4 inducing or inhibiting medications	Torisel® mRCC / MCL	Safety	repeat table 3.1-1.1 by subgroups according to CYP3A4 inducing or inhibiting medication (if number of patients with these medications is sufficiently large
3.1-2	All adverse events (by patients)	All	Safety	Incidence rates overall and for Primary System Organ Classes (PSOC) and preferred terms of MedDRA (non-serious/serious as columns) 1 total 2 by treatment sequence 3 by line
3.1-3	AE by severity (NCI-CTC grade)	All	Safety	Incidence rates overall and for PSOC and preferred terms of MedDRA severity: max. NCI-CTC grade within patient, PSOC, preferred term resp.(non-serious/serious as columns)
3.1-4	AE with relationship to study drug	All	Safety	Incidence rates overall and for PSOC and preferred terms of MedDRA (non-serious/serious as columns)
3.1-5	AE with action taken "Study medication permanently discontinued"	All	Safety	Incidence rates overall and for PSOC and preferred terms of MedDRA (non-serious/serious as columns)
3.1-6	AE by outcome (event basis)	All	Safety	Number of events overall and for PSOC and preferred terms of MedDRA
3.1-7	Treatment emergent AE: action taken (event basis)	All	Safety	Number of events overall and for PSOC and preferred terms of MedDRA
3.2	Deaths, other serious and significant adverse events			
3.2-1.1	Listing of deaths	All	Safety	Sorted by patient
3.2-1.2	Reason for death	All	Safety	Frequency table
3.2-1.3	Listing of serious adverse events (SAE, except deaths)	All	Safety	Sorted by patient

Table No.	Title	Treatment/ Indication	Analysis set	Description
3.2-1.4	Listing of SAE with outcome study treatment permanently discontinued	All	Safety	Sorted by patient
3.3	Laboratory values			
3.3-1	Hematology			
3.3-1	Laboratory values: hematology – study course	All	Safety	.x per parameter Sample statistics by visit, including difference and relative changes to baseline
3.3-2	Clinical chemistry			
3.3-2	Laboratory values: clinical chemistry- study course	All	Safety	.x per parameter Sample statistics by visit, including difference and relative changes to baseline
3.4	Global tolerability assessment			
3.4	Physician's global tolerability assessment	All	Safety	Frequency table by time windows and for the last documented visit
3.5	Vital signs, ECG, echocardiography and pain			
3.5-1	Course of blood pressure	mRCC	Safety	Sample statistics by time windows
3.5-2	Assessment of echocardiography	mRCC	Safety	Frequency table by visit
3.5-3	Course of pain	mRCC	Safety	Sample statistics by time windows
Listing	Listing of AE	All	Safety	
Listing	Data listing for patients included under Amendment VI	mRCC	All	demographic information, previous local and systemic therapy, duration of therapy (by Pfizer therapy, by non-Pfizer treatment), overall survival, progression free survival, course of Karnofsky performance scale, course of FKSI-15 and EQ-5D

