In total, the treatment of approximately 100 patients per year and product should be documented. This number of patients was chosen to capture a broad range of medical prescription habits and assess the target criteria as significantly as possible. The probability of occurrence of at least one "uncommon" (>1/1000, <1/100) AE is between 0.33 and 0.98 and for a "rare" AE (>1/10,000,<1/1000), between 0.04 and 0.33.

The planned number of 200 sites to be included according to Amendment III allows a representative cross-section across German oncology practices or clinics.

With Amendment VI, the efficacy of axitinib regarding the progression-free survival and overall survival is to be evaluated in the 3rd (and 4th) line of therapy and a correlation with patients on axitinib in the 2nd line of therapy is to be performed.

Patients already documented in STAR-TOR (n = 92; status of 06/30/2017) who received axitinib in the 2nd line of therapy, i.e. with a treatment course of sunitinib-axitinib, will be used as a (historical) comparison group for the comparison with the 3rd and 4th line of therapy, particularly because patients with axitinib in the 2nd therapy line are only rarely expected after the guideline amendments and therefore cannot be newly enrolled.

Patients already documented in STAR-TOR with axitinib in the 3rd line of therapy or 4th line of therapy should not be used to answer the expanded question (see above) as none of these patients received nivolumab or another active substance newly approved in 2016 in the 2nd line of therapy, but received other therapeutic options. It cannot be excluded that the deviating pretreatment/treatment course will impact the efficacy of axitinib in the subsequent lines of therapy as compared with current therapy guidelines.

[figure not shown]
Approximately 45 patients with a PFS event should be documented in the 3rd line with axitinib after the previous therapy sequence, e.g. sunitinib - nivolumab. Therefore, mPFS and mOS can be estimated with sufficient precision (see Statistical Analysis Plan). In order to recruit 45 new third-line axitinib patients after e.g. sunitinib-nivolumab pretreatment in STAR-TOR, approximately 45 months will be required (assuming the usual therapy periods).

Assuming that the last patient is enrolled after 45 months and a progression event (or death) occurs after approximately 6 months, a runtime of approximately 4 years should be assumed after implementation of Amendment VI.

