5 ANALYSIS SETS/POPULATIONS

Analyses will be performed within each indication and treatment, e.g. one for mRCC and temsirolimus, sunitinib and axitinib, one for the non-Pfizer interim therapies and one for MCL and one for GIST.

For data from mRCC patients included prior to amendment VI of the protocol baseline data from sequence 1 will be forwarded as baseline data for sequence 2, if the respective data is not asked for in follow-up 1 of sequence 2 (tumor anamnesis at time of primary diagnosis, prior local and systemic therapies, prior and concomitant diseases, concomitant medication (other than systemic therapy)). Ongoing adverse events from sequence 1 have to be added to the list of concomitant diseases in sequence 2. Additional cancer therapy from baseline and follow-up visits of sequence 1 will be forwarded as baseline data for sequence 2 unless the therapy has been discontinued.

For patients included under amendment VI, baseline data for the second Pfizer treatment will be asked for in the CRF as changes in this data are not completely asked for in the non-Pfizer treatment periods.

For data from mRCC patients the following tables (see chapter 9): demographic information (1.2-1; 1.2-2), study periods (1.1-5.2), previous local and systemic therapy (1.5-1; 1.5-2), duration of therapy (1.6-1), overall survival (2.2-1), progression free survival (2.3-1), course of Karnofsky performance scale (2.5) and course of FKSI-15 (2.6), EQ-5D (2.7) will be repeated for the following groups of patients:

- Treatment sequence 1^{st} sunitinib $\rightarrow 2^{nd}$ axitinib \rightarrow any further therapy
- Treatment sequence 1^{st} temsirolimus $\rightarrow 2^{nd}$ sunitinib \rightarrow any further therapy
- Treatment sequence 1^{st} sunitinib \rightarrow any further therapy (no axitinib in 2^{nd} line)
- Treatment sequence 1^{st} temsirolimus \rightarrow any further therapy
- Treatment sequence 1^{st} sunitinib \rightarrow no further therapy
- Treatment sequence 1^{st} temsirolimus \rightarrow no further therapy
- Any therapy $\rightarrow 2^{\text{nd}}$ axitinib \rightarrow any further therapy.

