8.1.2 Analysis Of Survival Data

OS, PFS and treatment duration will be analyzed using Kaplan-Meier plots. Median, 25% and 75% survival times with confidence intervals for OS and PFS will be presented. For stratification according to physician's prognosis and for risk groups according to Motzer score/MIPI/Fletcher risk table, log-rank tests will be performed.

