8.2 STATISTICAL ANALYSES

8.2.1 Summary of Efficacy/ Effectiveness Analyses

Not applicable

8.2.2 Safety Analyses

Adverse events will be analyzed giving absolute and relative frequencies in total and by MedDRA system organ classes and preferred term. Serious adverse events will be analyzed separately in the same manner.

Adverse events will presented within each treatment (temsirolimus, sunitinib, axitinib) and for all non-Pfizer treatments in total and by treatment.

Additionally the absolute and relative frequency of patients with premature discontinuation will be presented in total and by reason for premature discontinuation.

Prior and concomitant medication will be presented showing frequency tables.

Laboratory results and ECG results will be presented by visit.

Physician's assessment of tolerability will be analyzed presenting sample statistics.

8.2.3 **Summary of Analyses**

Outcome	Analysis Set	Supports Protocol Objective Number	Subgroups	Statistical Method	Covariates/ Strata	Missing Data
Demographic characteristics: age, height, weight, BMI, sex	Safety, EAS	4	None	Sample statistics	None	Excluded
Incidence of treatment- emergent adverse events	Safety	3	Patients receiving CYP3A4 inducing concomitant medication (only patients treated with temsirolimus) Patients receiving CYP3A4 inhibiting concomitant medication (only patients treated with temsirolimus)	Rate by SOC and PT	Non-serious AE, serious AE	Excluded
Discontinuations due to AE	Safety	3	None	Rate by SOC and PT	None	Excluded
Discontinuation from Study	Safety	3	None	Rate for reason for discontinuation	None	Excluded
Serious Adverse Events	Safety	3	None	Rate by SOC and PT	None	Excluded
Deaths	Safety	3	None	Rates for reason for deathListing of deaths	None	Excluded
Laboratory values	Safey	3	None	Sample statistics by parameter and visit	None	Excluded

Outcome	Analysis Set	Supports Protocol Objective Number	Subgroups	Statistical Method	Covariates/ Strata	Missing Data
Global tolerability assessment	Safety	2	None	Frequency table	None	Excluded
Overall survival	EAS	1	- 1 st line patients	Kaplan-Meier estimates; Kaplan- Meier curves; Log-rank test	 indication mRCC, GIST, MCL risk prognosis line of treatment low vs. high LDH response to prior therapy age groups (≤65 yrs; > 65 yrs) 	

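### SAP Table 2.2-2 (mRCC) plans a log-rank test of overall survival by drug and line, with no rule that keeps each patient in one group

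*SAP*

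**What the plan says.** **The table.** SAP section 9, Table 2.2-2 (mRCC, effectiveness set), gives eight groupings for overall survival (OS). The fifth and sixth read "5 by treatment sequence .6 by treatment and treatment line". After the eighth comes "incl. Log-ranktest and Kaplan-Meier curves". The table does not define membership of either grouping.

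**Where log-rank tests apply.** The SAP gives three accounts:
- Section 8.1.2 names physician's prognosis and "risk groups according to Motzer score/MIPI/Fletcher risk table, log-rank tests will be performed". Drug, line and sequence are absent.
- The OS row of the section 8.2.3 summary gives "Kaplan-Meier estimates; Kaplan- Meier curves; Log-rank test", and line of treatment is among its strata. Sequence is not.
- Table 2.2-2 places the test in the cell that holds both groupings.

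**Sequence groups.** SAP section 5 has the only list of sequence groups to be analysed. It says certain tables "will be repeated for the following groups of patients" and gives seven groups. The survival tables it names are 2.2-1 and 2.3-1, neither of which carries a log-rank test.

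**Repeated patients.** Protocol section 11 allows two Pfizer lines to be documented for one mRCC patient. The SAP flow chart gives the second its own baseline visit. SAP Appendix 1 (A1.3) counts OS from the baseline visit, and its PFS rules cover a death in sequence 2 for a subject analysed in sequence 1.

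**The concern.** A log-rank test compares groups of different people, and its variance assumes that the groups are independent. If the same patient is in the first-line sunitinib group and the second-line axitinib group, one death can count in both. The two contributions are positively correlated, so the stated variance is too large for a two-group contrast.

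There is a second issue. If OS restarts at the second baseline, a shared patient's OS from sequence 1 equals the gap between the two baselines plus OS from sequence 2. The first is longer by construction, whatever the drugs do.

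The registry plans a comparison of the three drugs (Protocol section 11, discussion of bias) and publication (Protocol 12.1). A p-value printed beside these curves would be read as evidence about drug and line.

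**Working it through.** The documents give no alpha, event count or p-value for these tests, so there is no planned figure to reproduce. A two-sided 5% level is assumed.

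**1. Can a patient be in two groups under item .6?** Yes, as written. Two Pfizer lines can be documented for one patient, the item groups by drug as well as line, and no sentence selects one line per patient.

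**2. Can a patient be in two groups under item .5?** Only if the section 5 list is used. Two pairs there are nested:
- sunitinib then second-line axitinib lies inside any therapy then second-line axitinib;
- temsirolimus then sunitinib lies inside temsirolimus then any further therapy.

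Only the first-line sunitinib group with further therapy carries an exclusion: "any further therapy (no axitinib in 2"nd line). The temsirolimus group has none.

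**3. How many patients might be shared?** The Protocol's case number estimate reports "Patients already documented in STAR-TOR (n = 92; status of 06/30/2017) who received axitinib in the 2nd line of therapy", after sunitinib. This is a ceiling on the sunitinib-axitinib overlap at that date. Protocol 7.2(c) admits patients at axitinib after earlier sunitinib, and section 11 lists axitinib as a possible first Pfizer sequence and bars documenting earlier courses. Such patients have only one registry sequence before any later one. The true overlap is not given.

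**4. Size under equal survival, item .6.** Take groups of n1 and n2 with m shared patients whose log-rank scores have correlation r. Approximately:

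true variance / assumed variance = 1 − 2mr/(n1 + n2)

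The SD of Z is the square root of this ratio, and rejection at nominal 5% is 2{1 − Φ(1.96/SD)}. With n2 = 92 and the other inputs assumed:

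| n1 | m | r | Variance ratio | SD | Rejection | Simulated |
|---|---|---|---|---|---|---|
| 200 | 92 | 0.95 | 1 − 174.8/292 = 0.401 | 0.63 | 0.2% | about 0.6% (SD 0.67) |
| 400 | 92 | 0.95 | 1 − 174.8/492 = 0.645 | 0.80 | 1.5% | SD 0.83 |
| 200 | 92 | 0.5 | 1 − 92/292 = 0.685 | 0.83 | 1.8% | 2.2% |
| 400 | 92 | 0.5 | 1 − 92/492 = 0.813 | 0.90 | 3.0% | 3.0% |
| 200 | 46 | 0.5 | 1 − 46/292 = 0.842 | 0.92 | 3.3% | 4.0% |
| 400 | 46 | 0.5 | 1 − 46/492 = 0.907 | 0.95 | 4.0% | 4.3% |

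The simulations used exponential OS with median 24 months, uniform censoring from 12 to 96 months, and r as the correlation of the latent survival times. Censoring weakens the correlation of the scores, so the simulated rates sit at or slightly above the formula.

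A second set had median 20 months, censoring from 6 to 60 months, all 92 shared and correlation 0.5 or 0.8:
- n1 = 200: 2.4% and 1.4%;
- n1 = 400: 4.4% and 2.4%;
- n1 = 92 (every first-line patient shared): 1.2% and 0.1%.

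Disjoint groups of 92 and 92 gave 5.4%, so the simulation behaves as it should.

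**5. Size under equal survival, item .5, if nested groups are tested in pairs.** With a subset of n1 and n2 further patients in the larger group, the ratio becomes n2/(2·n1 + n2):
- 92 within 184: 92/276 = 0.333, SD 0.58, rejection about 0.07%;
- 92 within 392: 300/484 = 0.620, SD 0.79, rejection about 1.3% (simulated 1.4%).

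One global test over all seven overlapping groups gave 5.1% to 6.0%, against 5.2% to 6.0% for seven disjoint groups, so no clear distortion.

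**6. Time origin.** Steps 4 and 5 assume equal survival distributions. If OS restarts at sequence 2, that equality fails for shared patients by the length of the gap. If OS is always counted from registry entry, the shared patient brings the same survival time to both groups. Independence fails either way.

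**The case against.** The strongest objection is that the overlap is inferred. Table 2.2-2 does not define its groups. SAP section 5 says analyses run within each indication and treatment, and section 9 repeats tables for each such combination unless specified otherwise. If item .6 means lines within one drug, a sunitinib-then-axitinib patient appears once under each drug and is never compared with himself. This reading is possible, but item .6 names treatment as a grouping factor, which would be redundant in a table already split by drug. The objection is stronger for Table 2.3-2, where "PFS 1st line vs. 2nd line and higher" reads naturally as lines within one drug. That PFS test is not part of this point.

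It also stands that section 8.1.2 does not extend log-rank tests to line or sequence. The section 8.2.3 summary does so for line, and Table 2.2-2 appears to for both, so the SAP disagrees with itself.

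A reader might infer three stronger things that the documents do not support:
- **That the sequence tests certainly use nested groups.** The section 5 list is tied to tables without a test, and grouping by each patient's complete sequence would be disjoint.
- **That 92 patients are known to be counted twice.** That figure is only a ceiling.
- **That all these p-values are badly wrong.** At moderate overlap and correlation the test is close to nominal, and the global seven-group test kept its size.

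Finally, the Protocol calls the evaluation purely descriptive, and the SAP has no hypotheses or decision rules. That limits the consequence, but a planned p-value should still be valid.

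**Conclusion.** The point holds for item .6 with medium confidence, and conditionally for item .5. As written, nothing stops one mRCC patient from entering two of the groups in a log-rank test.

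Under equal survival, with 92 axitinib patients, 200 to 400 first-line patients, 46 to 92 shared and correlation 0.5 to 0.95, a nominal 5% two-group test rejects in about 0.6% to 4%. It is conservative, and the low end needs complete overlap with very high correlation. Every input except 92 is assumed.

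The time-origin problem is separate. If OS restarts at sequence 2, the comparison is shifted towards longer OS in the earlier line, so the test cannot be called conservative overall. The documents do not give the gap between sequences, so this shift cannot be sized.

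No decision rule rests on these tests. The harm is a published p-value that does not mean what it says.

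**What to change.** 1. For items .5 and .6 of Table 2.2-2 (mRCC), choose one of the following:
   - mutually exclusive groups for any test, by each patient's complete sequence or by lines within one drug;
   - a Cox model with variance clustered on patient in place of the log-rank test;
   - no test, keeping the Kaplan-Meier curves as description.
2. State the time origin for OS in sequence 2, and do not test across different origins for the same patient. Clustered variance corrects the standard error but not this shift.
3. Say which groups item .5 uses. If it is the section 5 list, remove the two nestings before any test.
4. Make sections 8.1.2, 8.2.3 and 9 agree on where log-rank tests apply.

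The cost is SAP wording and minor programming, with no new data. If each patient is counted once, the later-line groups become smaller. Counting only the first registry sequence would remove patients who reached axitinib as their second sequence, so complete-sequence or within-drug grouping loses less.
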